11.5.8.1 Serious Adverse Events

Serious adverse events are those events that result in, or have potential to cause, either permanent impairment of an ocular function or damage to an ocular structure, and may necessitate medical or surgical intervention.

Serious adverse events may include any hazardous, **sight-threatening conditions** occurring after exposure to the test article, including the following:

- A presumed infectious ulcer (defined as a progressive erosion of the corneal tissue). For the purposes of reporting:
 - central or paracentral location;
 - penetration of Bowman’s membrane;
 - infiltrate ≥ 2 mm diameter;
 - associated with iritis Grade 2 or greater;
 - associated with any increase in intraocular pressure;
 - culture positive for microorganisms;
 - increasing size or severity at subsequent visits.
- Note: Signs of a presumed infectious corneal ulcer may include irregular focal infiltrates; active lesions with raised edges; significant diffuse infiltration; anterior corneal to

mid-stromal involvement; erosion with overlying staining; conjunctival and lid edema; anterior chamber reaction (iritis); severe bulbar and limbal redness. Symptoms associated with a presumed infectious ulcer (microbial keratitis) may include pain of rapid onset; severe redness; purulent or mucopurulent discharge; tearing; photophobia.

- Any central or paracentral (within 6 mm of cornea) corneal event that results in permanent opacification (such as vascularization);
- Any serious adverse ophthalmic events including hypopyon and hyphema;
- Any neovascularization within the central 6 mm of the cornea;
- Permanent loss of 2 or more lines of BSCVA;
- All cases of iritis.

[figure not shown]
11.5.8.2 Significant Non-Serious Adverse Events

Significant Non-Serious Adverse Events should include:

- Peripheral non-progressive non-infectious corneal ulcers;
- All symptomatic corneal infiltrative events;
- All cases of corneal staining greater than or equal to Grade 3;
- A temporary loss of 2 or more lines of BSCVA (for greater than or equal to 2 weeks);
- Neovascularization cases equal to Grade 2 or greater;
- Any ocular event that necessitates temporary lens discontinuation of greater than or equal to 2 weeks.

11.5.8.3 Adverse Event Treatment [REDACTED]

With any AE, treat the subject as appropriate to prevent further complications and to potentially resolve the event consistent with the standard of care.

11.5.8.4 Medical Treatment Including non-Adverse Events

In the event that a subject requires medical treatment (prescription medication) for an ocular condition, treat the subject as appropriate to prevent further complications and to potentially resolve the event.

11.5.8.5 Evaluations

When evaluating AEs, the Investigator must determine if the event is serious (refer to [Section 11.5.8.1](#) for criteria), assess the severity of symptoms and the relationship of the event to the study device using the following guidelines:

a. Severity

- **Mild:** Subject awareness of a sign or symptom that is easily tolerated, requires no treatment, and does not interfere with subject's daily activities.
- **Moderate:** Subject awareness of a sign or symptom which may be a low level of concern to the subject and may interfere with daily activities, but can be relieved by simple therapeutic care.
- **Severe:** A sign or symptom that interrupts the subject's daily activity and requires systemic therapy or other treatment.

b. Relationship to Study Device and/or Rewetting Drops

- **Related:** There is at least a reasonable possibility that the AE/SAE is related to the study device and/or Rewetting Drops. Reasonable possibility means that there is evidence to suggest a causal relationship or association between the study device and/or Rewetting Drops and the AE. Also referred to as an ADE.
- **Unrelated:** There is little or no reasonable possibility that the AE/SAE is related to the study device and/or Rewetting Drops. This assessment implies that the AE/SAE has no evidence to suggest either a causal relationship or association to the study device and/or Rewetting Drops and more likely or certain an alternative etiology exists.

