11.5.5 Change in Manifest Refraction Between the Screening and Exit Visits

11.5.6 Change in Corneal Curvature Between the Screening and Exit Visits

11.5.7 Adverse Event Definitions

- Adverse Event (AE): any untoward medical occurrence, unintended disease or injury, or untoward clinical signs (including abnormal laboratory findings) in a subject, user or other persons, whether or not related to the investigational medical device. This definition includes events related to the investigational medical device, comparator or the procedures involved. For users or other persons, this definition is restricted to events related to investigational medical devices.
- Adverse Device Effect (ADE): an AE related to the use of an investigational medical device. This definition includes AEs resulting from insufficient or inadequate instructions for use; deployment, implantation, installation, or operation; or any malfunction of the investigational medical device. This definition also includes any event resulting from use error or from intentional misuse of the investigational medical device.
- Serious Adverse Event (SAE) is an AE that:
 - led to death;
 - led to serious deterioration in the health of the subject, that resulted in:
 - a life-threatening illness or injury; or
 - a permanent impairment of a body structure or a body function (eg, blindness); or
 - in-patient or prolonged hospitalization; or
 - medical or surgical intervention to prevent life-threatening illness or injury or permanent impairment to a body structure or a body function;
 - led to fetal distress, fetal death, or a congenital abnormality or birth defect.

NOTE: Planned hospitalization for a pre-existing condition, or a procedure required by the protocol, without serious deterioration in health, is not considered an SAE.

- Unanticipated Adverse Device Effect (UADE): any serious adverse effect on health or safety or any life-threatening problem or death caused by, or associated with a device, if that effect, problem or death was not previously identified in nature, severity or degree of incidence in the investigational plan or application (including a supplementary plan or application), or any other unanticipated serious problem associated with a device that relates to the rights, safety, or welfare of subjects.

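### Section 11.5.8.5 has seriousness judged by an ocular-only definition that conflicts with the general SAE definition in Section 11.5.7, so non-ocular serious events can be flagged non-serious

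*Combined protocol and SAP*

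**What the plan says.** The protocol defines a serious adverse event twice and then tells the Investigator which definition to use.

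- Section 11.5.7 (Adverse Event Definitions) gives a general definition: death; serious deterioration in health through life threat, permanent impairment, "in-patient or prolonged hospitalization" or intervention to prevent such harm; and fetal or congenital harm. It is not limited to the eye.
- Section 11.5.8 says that AEs include serious and significant non-serious events, and that both are defined in the text that follows. It does not point back to Section 11.5.7.
- Section 11.5.8.1 describes serious events as those that cause, or could cause, "either permanent impairment of an ocular function or damage to an ocular structure, and may necessitate medical or surgical intervention". The examples are all ocular; one is "Any serious adverse ophthalmic events including hypopyon and hyphema".
- Section 11.5.8.2 lists the significant non-serious events. All of these are ocular too.
- Section 11.5.8.5 gives the working instruction, which begins "When evaluating AEs, the Investigator must determine if the event is serious (refer to" and names Section 11.5.8.1 as the source of the criteria. Section 11.5.7 is not mentioned.

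**The concern.** The seriousness decision controls what happens next. Under Section 11.5.8.6, serious and significant non-serious events go to the Medical Monitor within 24 hours. Under Section 12.3.3.2, subjects with a serious event are counted by treatment group, and Section 12.3.3.3 lists SAEs. If the decision is made against an ocular-only test, a non-ocular event that meets Section 11.5.7 can enter the database with the wrong flag and without the 24-hour report. With about 13 sites, one site working from Section 11.5.7 and another from Section 11.5.8.1 could classify the same event differently. Safety is part of the study objective (Section 6.1), so the serious-event summary should rest on one definition.

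**Working it through.** No arithmetic decides this point. The check sets the criteria side by side and then follows a non-ocular event through the procedure.

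**Step 1. Compare the criteria.**

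| Criterion in Section 11.5.7 | Counterpart in Section 11.5.8.1 |
|---|---|
| Death | None |
| Life-threatening illness or injury | None |
| Hospitalisation | None |
| Permanent impairment of body structure or function | Ocular form only |
| Intervention to prevent life threat or permanent impairment | Ocular form only |
| Fetal or congenital harm | None |

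The wording that introduces the examples in Section 11.5.8.1 makes the list non-exhaustive. That does not help a non-ocular event, because the lead definition above the list is itself ocular.

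**Step 2. Follow an unplanned non-ocular hospitalisation.**

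1. Section 11.5.7: it is an SAE. The note there excludes only planned hospitalisation for a pre-existing condition, or a procedure that the protocol requires, without serious deterioration in health. Hospitalisation was therefore meant to be a working criterion.
2. Section 11.5.8.5 sends the Investigator to Section 11.5.8.1. The event involves no ocular function or structure, so it is not serious by that test.
3. Section 11.5.8.2: no item applies, so it is not a significant non-serious event either.
4. Section 11.5.8.6: the 24-hour report is triggered by a serious event, a significant non-serious event or a medical treatment. Section 11.5.8.4 describes medical treatment as prescription medication for an ocular condition. None of the three triggers applies.
5. Sections 12.3.3.2 and 12.3.3.3: without the serious flag, the event is left out of the serious-AE count and the SAE listing.

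A non-ocular life-threatening event that does not lead to death takes the same path. So does a non-ocular permanent impairment, or an intervention to prevent one.

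**Step 3. Check whether the rest of the plan intends an ocular-only concept.** It does not. Section 11.5.8.6 allows a pregnancy complication to be recorded as an AE or an SAE, a distinction that Section 11.5.8.1 cannot make. Section 12.3.3 codes AEs in MedDRA and tabulates them over all system organ classes.

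**Step 4. Scale.** The documents give no SAE rate, so no expected count can be derived. Planned follow-up on lenses is about 244 × 3/12 = 61 subject-years before dropout.

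**The case against.** The strongest reply is that Section 11.5.7 is the definitions section, nothing later withdraws it, and Section 11.5.8.1 can be read as adding to it. A careful Investigator could apply both. The SAE/UADE reporting form is not among the documents and may carry the general criteria. This reply shows that misclassification is not certain. It does not remove the conflict, because the explicit instruction names only Section 11.5.8.1, and that section does not say it is a supplement.

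A reader might also infer more serious consequences, and here the other side is largely right:

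- *Deaths would disappear.* The outputs do not allow that. Section 12.3.3.3 lists deaths in their own right, and Section 12.3.3.2 tabulates AEs leading to death separately.
- *Pregnancy outcomes would be missed.* Section 11.5.8.6 gives serious pregnancy complications their own 24-hour route on the SAE/UADE form.
- *Expedited sponsor reporting would fail generally.* Section 11.5.9 limits it to product-related SAEs and to UADEs. An unrelated hospitalisation would not be expedited under either definition. The UADE definition in Section 11.5.7 covers previously unidentified life-threatening problems and deaths associated with the device, and it does not pass through Section 11.5.8.1.
- *Events would be lost altogether.* Section 11.5.8 requires AEs after consent to be reported, AEs are collected at every visit (Table 1), and Section 12.3.3.1 lists all reported AEs. Section 11.5.8 clouds this by glossing AEs, in parentheses, as the serious and significant non-serious ones. Even so, the likelier error is a wrong flag and a missing 24-hour report, not a missing event.

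**Conclusion.** The inconsistency is real and the rule is wrong as written. Sections 11.5.7 and 11.5.8.1 disagree on what is serious, and Section 11.5.8.5 directs the Investigator to the narrower one. The remaining exposure is non-ocular hospitalisation, non-ocular life-threatening events, and permanent impairment or preventive intervention outside the eye. For these, the seriousness flag, the 24-hour report and the serious-AE summary and listing can be wrong.

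The size cannot be computed from the documents. Few such events are likely in about 244 subjects over 3 months; that is a judgement, since no rate is given. The conclusion rests on sites following Section 11.5.8.5 literally and on the reporting form not correcting it. The mismatch in the text is certain; how often it would cause a misclassification is not. The primary analysis of visual acuity at 1 week does not use the seriousness flag. The point still merits correction, because the change is small and it affects safety reporting.

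**What to change.** Reconcile the three sections so that seriousness has one consistent set of criteria:

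1. In Section 11.5.8.5, refer to both Section 11.5.7 and Section 11.5.8.1, and state that an event meeting either is serious.
2. Open Section 11.5.8.1 by saying that its ocular events are reported as serious in addition to the criteria in Section 11.5.7.
3. In Section 11.5.8, align the sentence that says where the categories are defined, so that it also leads to Section 11.5.7.

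The cost is a few sentences in the protocol and a line in site training. The downside is a few more SAE reports. No new clinical rule is introduced, because the general criteria are already in the protocol.

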9.2 Concomitant Medications

Subjects will be instructed to use their habitual rewetting drops as needed during the study. Other contact lenses/solutions are not allowed to be used by subjects during the study. All concomitant medications (ocular, systemic or topical) that have been taken in the past 30 days before signing the ICF and during the course of the study will be collected.

In the event that a subject requires medical treatment (prescription medication) for an ocular condition, treat the subject as appropriate to prevent further complications and to potentially resolve the event.

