11.5.8 Adverse Event

Throughout the course of this study, all efforts will be made to remain alert to possible AEs. The term “AEs” includes both SAEs and Significant Non-Serious Adverse Events. Each are defined below.

If an AE occurs, the first concern will be the safety of the subject and appropriate medical intervention will be made. All AEs (serious AEs and significant non-serious AEs) that occur will be reported in this study.

AEs should be differentiated into device related and non-device related. Any corneal infiltrate, ulcer, neovascularization, etc. shall be presumed to be device related, in the absence of an alternative explanation.

All AEs occurring after signing of informed consent and through the subject’s end of participation in the study must be reported. All AEs must be followed until the event resolves or stabilizes.

All AEs should be photo documented and communicated to the CRO and Sponsor in electronic form.

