11.5.8.6 Procedures for Reporting Adverse Events and Serious Adverse Events

In the case of an AE (Serious and Significant Non-Serious) or Medical Treatment (non-AE), the Investigator must:

- Report the AE or Medical Treatment to the Medical Monitor within 24 hours of knowledge of the event using the Sponsor-provided form (SAE/UDE reporting form) by emailing the completed form to the Medical Monitor

- Indicate on the Initial SAE/UADE reporting form whether the SAE/UADE is presumed to be not study-related, lens-related, solution-related, or both lens/solution related.
- Ensure that the subject's identity is protected and the subject's identifiers in the clinical trial are properly mentioned on the form.
- BEGIN TREATMENT OF THE AE IMMEDIATELY BY A SUITABLY LICENSED EYE CARE PROFESSIONAL.
- Enter the SAE/UADE into the eCRF within 3 business days of submitting the Initial AE/Medical Treatment Notification Form.
- Continue to update the eCRF, if applicable, each time the subject is seen during the management of the incident and at resolution of the incident. Whenever possible, it is suggested that the Investigator take photographs of all AEs and forward them to the Sponsor.
- Cases requiring medical treatment will be evaluated by the Sponsor. Upon review of the medical treatment, Bausch + Lomb Clinical Operations representatives may contact the Investigator to request further information concerning the treatment.
- Submit all bills, prescription receipts, and culture reports/fees related to the AE to Bausch + Lomb Clinical Operations. Expenses incurred for study-related medical treatment will be paid by Bausch + Lomb Clinical Operations.

Guidelines for Reporting Pregnancies

All female subjects of childbearing potential must use an effective method of birth control during the study, to include 2 weeks after last visit, in a manner such that risk of contraceptive failure is minimized. Abstinence is allowed as a birth control method. Before enrolling a female subject of childbearing potential, the Investigator must review the following information about study participation:

- Informed consent requirement
- Contraceptives in use

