- Allergic reactions of ocular surfaces or adnexa that may be induced or exaggerated by wearing contact lenses or use of contact lens solutions.
- Ocular irritation due to allergic reactions which may be caused by use of contact lens solutions (i.e., rewetting drops) that contain chemicals or preservatives (such as mercury, Thimerosal, etc.) to which some people may develop an allergic response.
- Any active corneal infection (bacterial, fungal, protozoal, or viral).
- If eyes become red or irritated.

WARNINGS

Patients should be advised of the following warnings pertaining to contact lens wear:

EYE PROBLEMS, INCLUDING CORNEAL ULCERS, CAN DEVELOP RAPIDLY AND LEAD TO LOSS OF VISION. IF THE PATIENT EXPERIENCES:

- Eye Discomfort,
- Excessive Tearing,
- Vision Changes,
- Loss of Vision,
- Eye Redness, or
- Other Eye Problems,

THE PATIENT SHOULD BE INSTRUCTED TO IMMEDIATELY REMOVE THE LENSES AND PROMPTLY CONTACT THE EYE CARE PROFESSIONAL.

- When prescribed for daily wear, patients should be instructed not to wear their lenses while sleeping. Clinical studies have shown that when lenses are worn overnight, the risk of ulcerative keratitis is greater than among those who do not wear them overnight.³
- Studies have shown that contact lens wearers who are smokers have a higher incidence of adverse reactions than nonsmokers.
- Problems with contact lenses or lens care products could result in serious injury to the eye. Patients should be cautioned that proper use and care of contact lenses and lens care products are essential for the safe use of these products.

- The overall risk of ulcerative keratitis may be reduced by carefully following directions for lens care.

⁷New England Journal of Medicine, September 21, 1989; 321 (12), pp. 773-783.

Specific Instructions for Use and Warnings:

- **Water Activity**

Instruction for Use

Do not expose contact lenses to water while wearing them.

WARNING:

Water can harbor microorganisms that can lead to severe infection, vision loss, or blindness. If lenses have been submersed in water when participating in water sports or swimming in pools, hot tubs, lakes, or oceans, the patient should be instructed to discard them and replace them with a new pair. The Eye Care Professional should be consulted for recommendations regarding wearing lenses during any activity involving water.

PRECAUTIONS

Special Precautions for Eye Care Professionals:

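### Section 11.5.8.5 labels an event due only to the subject's own rewetting drops an adverse device effect, contrary to the protocol's own definition and to its separate lens/solution attribution

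*Combined protocol and SAP*

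**What the plan says.** Section 11.5.8.5 tells the Investigator to "assess the severity of symptoms and the relationship of the event to the study device using the following guidelines". That lead-in names the study device and nothing else. The scale beneath it, however, covers the device and the rewetting drops together. An event is Related when "There is at least a reasonable possibility that the AE/SAE is related to the study device and/or Rewetting Drops", and the definition ends "Also referred to as an ADE". Unrelated is defined against the same combined exposure.

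Four other places bear on this:

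- Section 11.5.7 defines the term: "Adverse Device Effect (ADE): an AE related to the use of an investigational medical device". Drops are not mentioned.
- Section 11.5.8 states that "AEs should be differentiated into device related and non-device related".
- Section 11.5.8.6 has the Investigator indicate on the initial form whether the SAE/UADE is "presumed to be not study-related, lens-related, solution-related, or both lens/solution related".
- Section 9.2 says "Subjects will be instructed to use their habitual rewetting drops as needed during the study". Section 10.4 repeats this under the heading for noninvestigational products.

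Section 11.5.9 makes expedited reporting depend on relationship to the Test Product. Sections 12.3.3.2 to 12.3.3.4 set out the adverse event summaries and listings, and none of them uses relationship.

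**The concern.** Whether events are attributable to the lens is a basic safety question. Safety is part of the objective in section 6.1, and section 7.1 says the study is meant for submission to the Chinese authorities. The causality item is where that question is answered event by event. As worded, it cannot tell a lens effect from an effect of a product the sponsor neither supplies nor standardises, yet a Related answer carries a label that the protocol reserves for the device.

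A drop-only event is a realistic possibility. The Control lens guide in Appendix C has a contraindication that begins "Ocular irritation due to allergic reactions which may be caused by use of contact lens solutions (i.e., rewetting drops". That gives no rate for this trial, but it shows that the trial's own documents recognise the drops as a separate cause.

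At stake is consistency: the same event could be an ADE in one record and not in another, and nothing says which record governs.

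**Working it through.** No arithmetic applies, because the plan attaches no figure to this point. The check is to take each possible attribution and read off the classification that each section requires.

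| Investigator's view of the cause | 11.5.8.5 scale | ADE under 11.5.7? | 11.5.8 split | 11.5.8.6 form |
|---|---|---|---|---|
| Lens only | Related, ADE | Yes | Device related | Lens |
| Lens and drops | Related, ADE | Yes | Device related | Both |
| Drops only | Related, ADE | No | Non-device related | Solution |
| Neither | Unrelated | No | Non-device related | Not study-related |

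1. Three of the four rows agree across sections. The conflict is confined to the drops-only row, where an Investigator cannot follow section 11.5.8.5 and also satisfy sections 11.5.7 and 11.5.8.
2. The drops-only row is a separate category because section 10.4 classes the drops as noninvestigational. The presumption in section 11.5.8 that infiltrates and similar findings are device related does not close the gap, since it applies only when there is no alternative explanation.
3. The form supplies the missing distinction, but with two limits. The reporting procedure in section 11.5.8.6 opens with serious and significant non-serious events and also medical treatments, while the attribution item itself names only the SAE/UADE. Solution is also not defined. Since section 10.4 bars other care products, the drops are the likely meaning, but the text does not say so.
4. The two scales do not match: two combined levels in section 11.5.8.5 against four separated levels on the form. No rule says which prevails or whether the form's answer enters the eCRF.
5. On the analysis side, section 12.3.3.2 tabulates treatment-emergent or post-treatment events by arm, system organ class and preferred term, with an overview by severity, seriousness, discontinuation and death. Sections 12.3.3.3 and 12.3.3.4 list deaths, SAEs and discontinuations. No row or listing there is defined by relatedness, so the mislabel changes none of them. The primary analysis in section 12.3.2 concerns visual acuity and is untouched.

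**The case against.** The best defence is that the protocol already asks for the distinction elsewhere. Section 11.5.8 limits the working term to serious and significant non-serious events, section 11.5.8.6 sends both to the Medical Monitor on one form, and that form separates lens, solution and both. A broad Related category also errs towards caution. If one lens leads to more drop use, the resulting events are arguably a consequence of that lens.

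Much of this stands, and it limits what can be concluded:

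- A reader might infer that lens-related events could never be separated from drop-related ones. The documents do not support that: for SAEs and UADEs the form's separation is explicit, and for significant non-serious events it is unclear rather than absent.
- A reader might infer that drop reactions would be counted as lens effects in the safety results. No planned table counts ADEs or related events, so there is no such count to inflate.
- A reader might infer that a drop reaction would go to authorities or review boards as a lens effect. No section says that the judgement in 11.5.8.5 drives reporting under 11.5.9, and for SAEs the form carries its own attribution.

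The defence does not remove the conflict in the drops-only row. Caution may justify a wide screening category, but it does not justify giving that category a label the protocol defines more narrowly.

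**Conclusion.** The rule in section 11.5.8.5 is wrong as written. It contradicts its own lead-in, the ADE definition in section 11.5.7 and the device/non-device split in section 11.5.8, and it does not match the scale in section 11.5.8.6. The consequence is modest. It falls on the classification of individual events attributed to drops alone, and on any listing or report that uses relatedness.

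The size cannot be estimated. The documents give no rate of drop use, of drop reactions or of related events. A reader might want a percentage overstatement of lens-related events, but any such figure would only restate an assumed drops-only share that has no source in the documents.

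The conclusion rests on reading section 11.5.8.5 as the rule Investigators will apply. The eCRF page and the SAE/UADE form are not in the documents, so it is possible that they already collect more than the text requires.

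**What to change.** - In section 11.5.8.5, replace the combined judgement with two yes/no items for every reported adverse event: related to the study lens, and related to rewetting drops.
- Derive ADE from the lens item alone, as section 11.5.7 already implies, and use the same item for the split in section 11.5.8.
- Put the same two items on the section 11.5.8.6 form, and state that they apply to serious and significant non-serious events alike.
- In section 11.5.9, state that relationship to the Test Product is taken from the lens item.
- In the section 12.3.3.2 overview, add the number and percent of subjects with lens-related treatment-emergent or post-treatment events, by arm. This is an addition to the planned reporting: it does not correct an existing table, but it would let the trial report lens-related events.

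The cost is wording changes, one table row and one extra attribution per event, with mixed cases recorded as yes to both. If the eCRF already holds two fields, the data collection does not change. Visits, treatment and sample size stay as they are.
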